10.4.2 Glaucoma and Other Medical/Surgical History

10.4.2.1 Glaucoma History

Presence of Chronic Primary Open Angle Glaucoma, Symptomatic Eyes, Primary Eye and Secondary Eye will be summarized for the SAF and listed for the ITT. A listing will present all recorded glaucoma history data including details of other diagnosis than chronic primary open angle glaucoma, if any.

10.4.2.2 Medical/Surgical History

[figure not shown]
The medical and surgical history terms will be coded to a PT and SOC.

Medical History will be summarized per treatment group and overall by absolute counts (n) and percentages (%) for the number of patients with at least one medical history event for the SAF. Percentages will be calculated based on the number of patients in the population.

A listing presents all reported medical history data based on the ITT.

Surgical History will be summarized per treatment group and overall by absolute counts (n) and percentages (%) for the number of patients with at least one surgical history event for the SAF. Percentages will be calculated based on the number of patients in the population.

A listing presents all reported surgical history data based on the ITT.

10.4.3 Prior/Concomitant Medications

Further to section 7.2.4, the 'Prior and Concomitant Medications' eCRF records information on total daily dose, dose unit and other dose unit and whether the medication is to treat eyes, and if so, which eyes are involved.

Prior and Concomitant medications will be summarized by treatment group and overall for the SAF separately on a per-patient basis (i.e. if a patient reported the same medications repeatedly the medications will be counted only once at the specific level of display). Absolute counts (n) and percentages (%) will be presented for the number of patients taking at least one medication and per WHO Drug class 2 (ATC therapeutic main class) and per WHO Drug Name (Preferred Term) within ATC Drug class 2. Percentages will be calculated based on the number of patients in the SAF.

A Listing will present all documented medication data for the ITT and will include a flag for Prior medication.

10.5 Exposure and Compliance to Study Medication

The exposure variables Duration of Treatment Period, Duration of Follow-up Period, Extent of Exposure and Days on Study Medication will be summarized for the SAF per treatment group.

Compliance will be summarized for the ITT as counts and percentages in categories as defined in section 7.2.5. The percentages will be based on the number of patients in the ITT.

All eCRF data related to the assessment of exposure and compliance will be listed for all patients in the ITT. In addition, all data recorded on eCRF page 'Administration of Study Drug' including details on first 2 doses of study drug administration at site and occurrence of immediate AEs will be listed for all patients in the ITT.

10.6 Primary Study Outcomes

10.6.1 Primary Safety Outcomes

The incidence of USPON, USPON during treatment period, Intolerance/Allergy to the drug, Unexpected Related AEs affecting ocular function/eye pressure, Local toxicities and systemic toxicities will be summarized for SAF by counts and percentages of affected patients per treatment group. In addition, number of reported events will be provided.

A listing will be provided for the SAF summarizing all incidences on the patient level. The original source of presented events will be flagged in respective listings for AEs, BCDVA, HVF, ERG and OCT, respectively.

10.6.2 Primary Tolerability Outcomes

The Overall VAS Ocular Tolerability Scores as well as the seven symptoms scores will be summarized per Primary/Secondary Eye and treatment group for the SAF at each scheduled study visit. In addition, Change from Baseline summaries will be provided together with respective inferential statistics for the SAF as described in section 8.2.

All data of tolerability will be listed for all patients of the SAF.

10.7 Secondary Explorative Efficacy Outcomes

All exploratory efficacy analysis will be performed on the ITT by Primary and Secondary Eye according to the treatment randomized.

10.7.1 Change in Best-Corrected Distance Visual Acuity

The Visual Acuity Score and logMAR are summarized per Primary/Secondary Eye respectively for each treatment group at all scheduled study visits and changes from baseline for Visual Acuity Score and LogMAR at week 8, week 12 and week 32.

No imputation for missing values will be performed for these analysis. For safety tables associated for BCDVA please refer to section 10.8.

A listing will be provided describing all recorded data as well as changes from baseline for the ITT.

10.7.2 Changes in Visual Field Testing

All HVF data will be listed for the ITT by date and eye including derived information on corresponding treatment period and occurrence of USPON. No changes from baseline will be calculated for these data.

10.7.3 Changes in ERG

PhNR results as well as changes from baseline will be summarized for Primary/Secondary Eye respectively for each treatment group at all scheduled visits.

A listing will present all recorded ERG results for the ITT flagging also records reflecting the occurrence of USPON due to ERG assessments.

10.7.4 Ocular Coherence Tomography (OCT)

All 17 (4+12+1) RNFL variables will be summarized by Primary/Secondary Eye for each treatment group at all scheduled visits as well as changes from baseline at Week 8, Week 12 and Week 32.

A listing will present the above variables over time for each eye as well as the changes from baseline for these variables for all patients in the ITT.

[figure not shown]
All nine variables associated with PanoMap analysis will be summarized by Primary/Secondary Eye for each treatment group at all scheduled visits and changes from baseline at Week 8, Week 12 and Week 32.

A listing will present all PanoMap assessments as well as the changes from baseline for all patients in the ITT.

All 6 variables associated with Ganglion Cell Analysis will be summarized by Primary/Secondary Eye for each treatment group at all scheduled visits and changes from baseline at week 8, week 12 and week 32.

A listing will present all Ganglion Cell Analysis results as well as the changes from baseline for all patients in the ITT.

All assessments associated with an USPON will be flagged in the 3 listings describing OCT results.

10.8 Adverse Events and Further Safety Assessments

10.8.1 Adverse Events

10.8.1.1 Brief Summary of Adverse Events

An overview summary will be provided for the SAF by presenting of events as well as number and percentages of affected patients for AEs, TEAEs, TEAEs in the Treatment Period, TEAEs in the Follow-Up Period, TEAEs leading to Premature Withdrawal of Study Treatment, TEAEs leading to Study Discontinuation, Treatment Related TEAEs, Serious AEs, Serious TEAEs, Treatment Related Serious TEAEs Fatal AEs, AESIs, TEAEs by severity, TEAEs in the Treatment Period by severity, TEAEs in the Follow-Up Period by severity, TEAEs by age category, TEAEs in the Treatment Period by age category, TEAEs in the Follow-Up Period by age category.

10.8.1.2 Display of Adverse Events

Adverse event descriptive tables will be summarized separately for each study treatment and overall.

They will be summarized on a per-patient basis (i.e. if a patient reported the same event repeatedly the event will be counted only once at the specific level of display). Absolute counts (n) and percentages (%) will be presented for the number of patients with at least one adverse event, and per SOC and per PT within SOC, for the SAF. Percentages will be based on the number of patients in the population. In addition, number of events will be provided.

Descriptive tables will be ordered by descending frequency of the overall number of patients within each SOC regardless of treatment group, and then ordered within each SOC by the overall number of patients within each PT regardless of treatment group. In the event of equal frequencies tables will be ordered by active treatment frequency and then alphabetically.

The following tables will be provided:

- AEs for the SAF
- TEAEs for the SAF
- Treatment related TEAEs for the SAF
- TEAEs leading to premature withdrawal of Study Treatment for the SAF
- TEAEs leading to study discontinuation for the SAF
- Serious TEAEs for the SAF
- TEAEs by severity for the SAF
- TEAEs by age category ('≤ 65 years' vs '>65 years') for the SAF
- TEAEs in the Treatment Period for the SAF
- TEAEs in the Treatment Period by severity for the SAF
- TEAEs in the Treatment Period by age category ('≤ 65 years' vs '>65 years') for the SAF
- TEAEs in the Follow-Up Period for the SAF-F
- TEAEs in the Follow-Up Period by severity for the SAF-F
- TEAEs in the Follow-Up Period by age category ('≤ 65 years' vs '>65 years') for the SAF-F

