11.5.4. Safety Analysis

Safety variables will be presented for the Safety population.

The primary safety endpoint in this study is Adverse Events (AEs). AEs will be recorded at the scheduled study visits and may also be recorded at any unscheduled visit that occurs during the study.

AEs will be presented, by treatment group, in terms of the incidence, severity and relationship to the study drug, overall and by SOC (System Organ Class) and preferred term. Serious AEs (SAEs) will be presented in the same way. All adverse events will be reported by MedDRA preferred term.

The following adverse event summary tables and listings will be provided:

Tables:

- Frequency and Incidence of Subjects with Adverse Events
- Frequency and Incidence of Subjects Discontinued Due to Adverse Events
- Frequency and Incidence of Subjects with Serious Adverse Events
- Adverse Events by Coded Adverse Event and SOC
- Overall Frequency and Incidence of Adverse Events
- Overall Frequency and Incidence of Adverse Events by Severity
- Overall Frequency and Incidence of Treatment-Related Adverse Events
- Overall Frequency and Incidence of Adverse Events Occurring at Rates Greater Than or Equal to 1.0%
- Overall Frequency and Incidence of Adverse Events by Age

Listings:

- Concomitant Diseases and Medications for Subjects with Adverse Events by Investigator and by Subject
- Coded and Descriptive Terms of Adverse Events by Investigator and by Subject
- Deaths, Other Serious or Clinically Significant Adverse Events
- Adverse Events by Investigator and by Subject

In addition to reporting of adverse events for any untoward (unfavorable and unintended) medical occurrences, adverse events will also be reported for any clinically relevant change from baseline in any assessment evaluated during the study, based upon an assessment by the Investigator.

Ocular tolerability as measured by the VAS will be analyzed by means of analysis of variance, including terms for treatment, time, and treatment by time interaction.

Best corrected distance visual acuity, external ocular examination, slit lamp examination, intraocular pressure, and dilated fundus ophthalmoscopy, will be presented with the appropriate descriptive statistics and shift tables will be used to present shifts from before and after treatment at each recording time points.

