6.1 Analysis Sets

Evaluability for all patients and visits will be determined during a Blind Data Review Meeting, which will take place before unmasking the study for the main objective analysis (i.e. comprising data up to Week 12 Visit).

The Total Set (TOT) will include all patients that have signed informed consent.

The Intent-to-treat Set (ITT) will include all randomized patients and will be used for all exploratory efficacy analyses. All analyses based on the ITT will be summarized by the treatment randomized.

The Safety Set (SAF) will include all randomized patients who receive at least one dose of study medication. This safety population will be used in the analysis of all safety endpoints.

A subset of all patients in the SAF, who entered the Follow-Up Period (SAF-F), will be used in addition to present event-type analyses of the Follow-Up Period. A patient will therefore be considered as entering the Follow-Up Period, if he/she did not terminated the study at or before the Week 8 visit.

All analyses based on the SAF and SAF-F will be summarized by the treatment received.

For the study, both eyes are under investigation. For each patient, a Primary (Study) Eye and a corresponding Secondary Eye will be defined during a Blind Data Review Meeting (BDRM) to enable a patient based presentation of statistical analyses.

For each patient, an eye will be considered as Primary Eye, if

- the eye was treated and
- the investigator considered this eye as qualifying eye.

If both eyes are considered as qualifying eye, the right eye will be chosen.

The other eye will then be considered as Secondary Eye, if the eye was treated. If the other eye was not treated with study medication, no Secondary Eye will be assigned for this patient.

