6.2 Subgroup Definitions

For the presentation of adverse events by age, age categories ' ≤ 65 years' and '>65 years' will be applied.

7 Definition of Time Points and Analysis Variables

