8.1 General Methods

For the study, both eyes are under investigation. For analysis purposes all eye-related assessments will be displayed separately by Primary/Secondary Eye. Untreated eyes will not be considered for analysis and be listed only indicated with 'Untreated'.

For continuous variables, the mean, standard deviation, minimum, median and maximum will be presented by treatment group, together with the total number of observations and the number of missing and non-missing values. Unless otherwise specified minimum and maximum values will be reported to the same number of decimal places as the recorded measurements, mean and median are reported to one more decimal place and standard deviation one additional decimal place more than the mean.

For categorical variables, absolute and relative frequencies will be reported by treatment group. Relative frequencies will be based on all observations and reported as a percentages to one decimal place. Unless otherwise specified, percentages will be based on the number of patients with data in the considered analysis set and will not be calculated for missing categories.

Incidences over a specific time interval like adverse events, medical history and concomitant medication will be reported on a patient basis. The percentages will be calculated using the number of patients in the treatment group for the considered analysis set as denominator. For the presentation of incidences during the Follow-Up Period, the SAF-F set will be used, which results in a reduction of the denominator to the number of patients in the SAF, who have entered the Follow-Up Period.

All hypotheses will be tested at a 5% level of significance using a two-sided test.

P-values will be rounded to three decimal places. If a p-value is less than 0.001 it will be reported as "<0.001." If a p-value is greater than 0.999 it will be reported as ">0.999.

Statistical significance will be declared if the rounded p-value will be less than 0.050 unless stated otherwise. Two-sided 95% confidence intervals of the differences between the treatment groups will be calculated as indicated in sections 8.2 and 8.3.

Post-Text TLFs will be provided in collated electronic MS Word .rtf files (i.e. table columns and rows appear as free text instead of MS Word Table format).

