10.8.5 Slit Lamp Examination

All grading assessments of different eye structure (excluding assessment for other structures) will be summarized descriptively by treatment group and study visit for the Primary Eye as well as the Secondary Eye. In addition, a shift table will be provided displaying the status of all scheduled post-baseline visits in relation to the baseline status. The percentages are based on the number of SAF patients in the respective baseline stratum of considered treatment group. These analyses will be performed on the SAF.

All data recorded on the eCRF page 'Slit Lamp Examination (Biomicroscopy)' will be listed for the SAF.

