Table 14.2-3.1	Summary of BCDVA Scores	ITT	U	Y
Table 14.2-3.2	Summary of Changes from Baseline in BCDVA Scores	ITT	U	Y
Table 14.2-3.3	Analysis of Changes from Baseline in BCDVA Scores	ITT	U	N
Table 14.2-4.1	Summary of LogMAR	ITT	U	Y
Table 14.2-4.2	Summary of Changes from Baseline in LogMAR	ITT	U	Y
Table 14.2-4.3	Analysis of Changes from Baseline in LogMAR	ITT	U	N
Table 14.2-5.1	Summary of PhNR	ITT	U	Y
Table 14.2-5.2	Summary of Changes from Baseline in PhNR	ITT	U	Y
Table 14.2-5.3	Analysis of Changes from Baseline in PhNR	ITT	U	N

TLF number	Title	Analysis Set	U/R	SR
Table 14.2-6.1	Summary of RNFL Variables	ITT	U	Y
Table 14.2-6.2	Summary of Changes from Baseline in RNFL Variables	ITT	U	Y
Table 14.2-6.3	Analysis of Changes from Baseline in RNFL Variables	ITT	U	N
Table 14.2-7.1	Summary of PanoMap Variables	ITT	U	Y
Table 14.2-7.2	Summary of Changes from Baseline in PanoMap Variables	ITT	U	Y
Table 14.2-7.3	Analysis of Changes from Baseline in PanoMap Variables	ITT	U	N
Table 14.2-8.1	Summary of Ganglion Cell Variables	ITT	U	Y
Table 14.2-8.2	Summary of Changes from Baseline in Ganglion Cell Variables	ITT	U	Y
Table 14.2-8.3	Analysis of Changes from Baseline in Ganglion Cell Variables	ITT	U	N
Table 14.3.1-01.1	Overall Summary of Adverse Events	SAF	U	Y
Table 14.3.1-02.1	Summary of Adverse Events by System Organ Class and Preferred Term	SAF	U	Y
Table 14.3.1-03.1	Summary of TEAEs by System Organ Class and Preferred Term	SAF	R	Y
Table 14.3.1-04.1	Summary of Treatment Related TEAEs by System Organ Class and Preferred Term	SAF	R	Y
Table 14.3.1-05.1	Summary of TEAEs leading to Premature Withdrawal of Study Treatment by System Organ Class and Preferred Term	SAF	R	Y
Table 14.3.1-06.1	Summary of TEAEs leading to Study Discontinuation by System Organ Class and Preferred Term	SAF	R	Y
Table 14.3.1-07.1	Summary of Serious TEAEs by System Organ Class and Preferred Term	SAF	R	Y
Table 14.3.1-08.1	Summary of TEAEs by Severity, System Organ Class and Preferred Term	SAF	U	Y
Table 14.3.1-09.1	Summary of TEAEs by Age Category, System Organ Class and Preferred Term	SAF	U	Y
Table 14.3.1-10.1	Summary of TEAEs in the Treatment Period by System Organ Class and Preferred Term	SAF	R	N
Table 14.3.1-11.1	Summary of TEAEs in the Treatment Period by Severity, System Organ Class and Preferred Term	SAF	R	N
Table 14.3.1-12.1	Summary of TEAEs in the Treatment Period by Age Category, System Organ Class and Preferred Term	SAF	R	N

TLF number	Title	Analysis Set	U/R	SR

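### Taken as written, the SAP divides adverse-event percentages by age category by the whole arm, so they are not incidences by age

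*SAP*

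**What the plan says.** Protocol 11.5.4 lists, among the required safety tables, "Overall Frequency and Incidence of Adverse Events by Age".

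SAP 6.2 sets the cut at 65 years ("For the presentation of adverse events by age, age categories" of 65 or under and over 65) but gives no denominator. SAP 10.8.1.2 plans three by-age tables: all TEAEs, TEAEs in the Treatment Period and TEAEs in the Follow-Up Period. In section 12 they are Tables 14.3.1-09.1 ("Summary of TEAEs by Age Category, System Organ Class and Preferred Term"), 14.3.1-12.1 and 14.3.1-15.1. The overview in SAP 10.8.1.1 (Table 14.3.1-01.1) also has age rows.

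Two passages fix the percentage base:

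- SAP 10.8.1.2, for all the adverse-event tables it lists: "Percentages will be based on the number of patients in the population".
- SAP 8.1, for incidences over a time interval, with adverse events named: "The percentages will be calculated using the number of patients in the treatment group for the considered analysis set as denominator". For follow-up it adds: "For the presentation of incidences during the Follow-Up Period, the SAF-F set will be used".

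The analysis sets in SAP 6.1 are TOT, ITT, SAF and SAF-F. None is split by age: "The Safety Set (SAF) will include all randomized patients who receive at least one dose of study medication". Protocol 11.5.1 likewise names only the analysis population and the treatment group.

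For the shift tables in SAP 10.8.4, 10.8.5 and 10.8.7 the plan does state a narrower base: "The percentages are based on the number of SAF patients in the respective baseline stratum of considered treatment group". Nothing comparable is stated for age.

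**The concern.** Age category is a baseline property of the patient. A patient over 65 can never contribute an event to the row for 65 or under, so that patient does not belong in its denominator. The by-severity tables are different: any patient can have an event of any severity, and there the whole arm is the right base.

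With the whole arm underneath, the printed figure mixes how often events occur in an age group with how many such patients were enrolled. Two comparisons suffer: younger against older patients within an arm, and rhNGF against vehicle within an age row. Safety is the primary objective and age is the only subgroup the SAP defines, so these are the tables a reader would consult on whether tolerability depends on age.

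**Working it through.** **Inputs from the documents.** Planned arms are 40 rhNGF and 20 vehicle (protocol synopsis; 60 patients at 2:1). The percentage base is the arm of the SAF or SAF-F (SAP 8.1 and 10.8.1.2). The plan states no figure on this point that could be reproduced.

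**Assumptions.** Neither the age mix nor the event rate is given. A true rate of 50% in both age groups is assumed unless stated otherwise, and the age mix is varied.

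**Formulas.** Let N be the arm size, n the number of its patients in the age group, and p the true incidence in that group.

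- Printed under the SAP rule: (n × p) / N = p × (n / N)
- Incidence by age: (n × p) / n = p
- Relative shortfall of the printed figure: 1 − n / N

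**1. Within an arm, equal true incidence (50%), rhNGF, N = 40**

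| Aged ≤65 / >65 | Printed ≤65 | Printed >65 | Ratio >65 : ≤65 |
|---|---|---|---|
| 28 / 12 | 35.0% | 15.0% | 0.43 |
| 20 / 20 | 25.0% | 25.0% | 1.00 |
| 16 / 24 | 20.0% | 30.0% | 1.50 |
| 12 / 28 | 15.0% | 35.0% | 2.33 |
| 8 / 32 | 10.0% | 40.0% | 4.00 |

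For the 12 / 28 row: 0.50 × 12/40 = 15% and 0.50 × 28/40 = 35%, which are 70% and 30% below the true 50%. Vehicle (N = 20) gives the same percentages at the same shares. With the age-group base every row reads 50% and 50%, for example 6/12 and 14/28.

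**2. Within an arm, unequal true incidence, 12 / 28 split**

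- True 6/12 = 50% and 7/28 = 25%: printed 6/40 = 15.0% and 7/40 = 17.5%. The order is reversed.
- True 9/12 = 75% and 7/28 = 25%: printed 9/40 = 22.5% and 7/40 = 17.5%. The order is kept, but a 3.0-fold ratio shrinks to about 1.3.

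The printed ratio of larger to smaller group is the true ratio multiplied by the size ratio (28/12 = 2.33). The larger group is therefore always inflated relative to the smaller. It overtakes the smaller one only when the smaller group's true rate is less than 2.33 times its own.

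**3. Between arms, within an age row, true 50% everywhere**

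- 16 of 40 rhNGF and 5 of 20 vehicle patients aged ≤65: printed 0.50 × 16/40 = 20.0% against 0.50 × 5/20 = 12.5%. For >65: 0.50 × 24/40 = 30.0% against 0.50 × 15/20 = 37.5%. These are expected values; the vehicle figures correspond to 2.5 and 7.5 patients.
- In whole patients, with 28 of 40 and 10 of 20 aged >65: 14/40 = 35.0% against 5/20 = 25.0%.

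The between-arm distortion vanishes only if the arms have the same age mix. The documents describe no stratification by age, and vehicle has only 20 patients, so an unequal mix is plausible.

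**The case against.** The strongest reply is that the SAP is silent rather than wrong. The rule in 10.8.1.2 is general, age sits under subgroup definitions, and the population of a subgroup table might mean the subgroup. The opening of SAP section 10 places the mock shells in a separate document, which was not available here. Section 12 marks Table 14.3.1-09.1 as unique, so it has its own shell, and that shell may show n per age group.

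This stands only in part. SAP 8.1 says what the base is for adverse-event incidences (the arm within the analysis set), and no section overrides it for age. Shells with age-group denominators would be sensible but would depart from the stated rule. SAP 5.3 checks tables against both SAP and templates, so the two would then conflict.

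The shift-table contrast is weak evidence of intent, because a shift table conditions on baseline status by construction. It shows that the plan can state a narrower base. A reader might infer that the authors deliberately chose the whole arm for age, but the documents do not show that.

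The point about limited impact stands in full. The tables are descriptive. SAP 8.2 foresees no inference even for the primary safety outcomes, and adverse events by age are not among them. Counts are printed beside the percentages, and age and events are listed per patient, so the correct figures can be recovered by hand. That takes some work: the demographic summary in SAP 10.4.1 specifies age in years and no count per age category.

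**Conclusion.** The point holds on the SAP text. Taken as written, the by-age percentages equal the incidence in the age group multiplied by that group's share of the arm, in the SAF for the whole-study and Treatment Period tables and in the SAF-F for the follow-up table. That is not the incidence by age that protocol 11.5.4 requests.

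With equal true incidence, the larger age group looks less safe, by a factor equal to the size ratio: 2.33 at 12 / 28, and none at 20 / 20. A reader might infer that the larger group always looks less safe. It does not, as the 9/12 against 7/28 example shows; what holds generally is inflation relative to the smaller group. A reader might also infer that the trial's main safety conclusions are compromised. The documents do not support that: overall incidences by arm and the primary safety outcomes do not use these denominators.

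All magnitudes rest on an assumed age mix and event rate, so they show what the rule can produce, not an expected error. The defect should be corrected before the tables are programmed, but it is confined to three descriptive tables and the age rows of the overview.

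**What to change.** Add to SAP 8.1 and 10.8.1.2: *For Tables 14.3.1-09.1, 14.3.1-12.1 and 14.3.1-15.1 and the age rows of Table 14.3.1-01.1, the denominator is the number of patients in that age category within the column shown (each treatment group, and both groups combined for the overall column), taken from the SAF, or from the SAF-F for follow-up rows.*

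Print that n in the column or row header and bring the mock shells into line. Naming the SAF-F also settles the follow-up age rows of the overview, which section 12 labels SAF while SAP 8.1 assigns follow-up incidences to the SAF-F. The by-severity tables keep the whole-arm base.

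The cost is one sentence in the SAP and a denominator change in three tables and the overview. No new data are needed.
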